5.1. Estimands

The analysis to address this objective has been developed in consideration of ICHE9(R1). Specifically, two intercurrent events have been identified: study drug discontinuation and death.

As to the study drug discontinuation, the "treatment policy" strategy will be applied to all efficacy endpoints (primary/secondary/exploratory) declared in Section 6 (apart from HAS and PGIS/PGIC). Efforts have been made to retain all patients in study follow-up, whether or not they have discontinued the study treatment. In view of the statistical analysis, methods for missing imputation will be applied in case of assessments not performed after study discontinuation (Appendix 12.1).

In the target population of patients with advanced NSCLC it is expected that death will be mostly due to the progression of the underlying malignant disease. The aim of anamorelin treatment is to increase body weight and improve anorexia symptoms while the patient is alive. Hence, it is necessary and sufficient to obtain regular assessments on body weight and anorexia symptoms between randomization and death. Therefore, a "while-on-treatment" type strategy for death (i.e. while alive) is applied.

HHELSINN

T AN001 Effective Date 25 JUL 2022 Approved Version 2.00

6. STUDY ENDPOINTS

6.1. Efficacy Endpoints

6.1.1. Primary Efficacy Endpoints

The co-primary efficacy endpoints are:

- Mean change in body weight from baseline over 12 weeks.
- Mean change in 5-item Anorexia Symptom Subscale (5-IASS) from baseline over 12 weeks.

6.1.2. Secondary Efficacy Endpoints

The secondary efficacy endpoints are:

- Duration of treatment benefit in weight gain (≥ 0 kg) over 12 weeks.
- Duration of treatment benefit in weight gain (≥ 1.5 kg) over 12 weeks.
- Duration of treatment benefit in anorexia symptoms (≥0 points) over 12 weeks, as measured by the 5-item Anorexia Symptom Subscale.
- Duration of treatment benefit in 5-item Anorexia Symptom Subscale (increase ≥ 3 points) over 12 weeks.
- Mean change in FAACT 12-item A/CS domain from baseline over 12 weeks.
- Mean change in FACIT-F 13-item subscore from baseline over 12 weeks
- Mean change in FAACT total score from baseline over 12 weeks.

6.1.3. Exploratory Efficacy Endpoints

- Mean change in body weight from baseline over 6, 9, 15, 18, 21, and 24 weeks.
- Mean change in patient-reported anorexia symptoms from baseline over 6, 9, 15, 18, 21, and 24 weeks, as measured by the 5-item Anorexia Symptom Subscale.
- Mean change in FAACT total score from baseline over 6, 9, 15, 18, 21, and 24 weeks.
- Composite Clinical Response (CCR) at Week 3, 6, 9, 12, 15, 18, 21, and 24.
- Change in body weight from baseline to Week 3, 6, 9, 12, 15, 18, 21, and 24.
- Change in patient-reported anorexia symptoms from baseline to Week 3, 6, 9, 12, 15, 18, 21, and 24, as measured by the 5-item Anorexia Symptom Subscale.
- Clinically meaningful gain in body weight (1.5 kg) from baseline to Week 3, 6, 9, 12, 15, 18, 21, and 24.
- Clinically meaningful increase in 5-item Anorexia Symptom Subscale (3 points) from baseline to Week 3, 6, 9, 12, 15, 18, 21, and 24.

- Percentage of change in body weight from baseline to Week 3, 6, 9, 12, 15, 18, 21, and 24.
- Changes from baseline to Week 3, 6, 9, 12, 15, 18, 21, and 24 in the FAACT total score, FACT-G total score, FAACT TOI, the 12-item A/CS domain and the 4-item Anorexia Concerns Subscale.
- Changes from baseline to Week 3, 6, 9, 12, 15, 18, 21, and 24 in the Functional Assessment of Chronic Illness Therapy-Fatigue (FACIT-F) domain as well as the FACIT-F TOI score.
- Changes from baseline to Week 3, 6, 9, 12, 15, 18, 21, and 24 in the Hunger Assessment Scale.
- Changes from baseline to Week 6 and 9 in the Patients' Global Impression of Severity (PGIS) scale and the Patients' Global Impression of Change (PGIC) scale at Week 6 and 9.
- Changes from baseline to Week 3, 6, 9, 12, 15, 18, 21, and 24 in the following items extracted from Physical Well-Being and Functional Well-Being domains:
 - GP1, GP7, GF5, GF6, GF7.

Life Sciences

- Changes from baseline to Week 3, 6, 9, 12, 15, 18, 21, and 24 in the following items extracted from the 12-item A/CS domain:
 - ACT1, ACT2, ACT4, ACT13.
- Changes from baseline to Week 3, 6, 9, 12, 15, 18, 21, and 24 in the following items extracted from the FACIT-F (Fatigue) questionnaire:
 - HI7, HI12, AN2, AN5, AN12.
- Correlation between Weight gain and improvement on the patient reported anorexia score from baseline to Week 3, 6, 9, 12, 15, 18, 21, and 24.
- Correlation between Weight gain and improvement on the patient reported anorexia score from baseline over 12 weeks.

6.2. Safety Endpoints

- Treatment-emergent adverse events (TEAEs) and serious adverse events (SAEs)
- Changes from Baseline in vital signs, ECG parameters and laboratory assessments (chemistry, hematology, and urinalysis)
- Shifts from Baseline in laboratory assessments, physical examination and ECG overall interpretation.
- Overall Survival
- Overall Response based on tumor assessment

T AN001 Effective Date 25 JUL 2022 Approved Version 2.00

7. STUDY METHODS AND STATISTICAL PRINCIPLES

7.1. Randomization

Central randomization (IWRS) was stratified by:

- Line of systemic anti-cancer treatment (i. first vs ii. second vs iii. third line or higher),
- Type of anti-cancer therapy (immunotherapy vs non-immunotherapy),
- Baseline score of 5-item Anorexia Symptom Subscale (≤10 vs >10).

7.2. Sample Size

At the time when the trial was initiated, the primary endpoint was the Composite Clinical Response (CCR) rate. The sample size was determined based on results obtained in patients participating to the previous trials (HT-ANAM-301 and HT-ANAM-302 (4), (5)). The retrospectively observed CCR rates, in the subset of patient with baseline BMI <20 kg/m² and ongoing problems with appetite/eating as defined by inclusion criterion 5, were 20% for anamorelin and 7.5% for placebo at week 12, and 21.0% vs. 6.0% at week 9.

To be conservative the study was adequately powered to detect an improvement in CCR Rate at week 9 from 7.5% in the placebo group to 20.0% for the anamorelin group. This improvement would be detected with 90% power, using a logistic regression for the CCR, with a sample size of 316 patients (158 patients per arm) and a 2-sided 0.05 significance level.

In the latest version (V5.0-V5.A) of the study protocol, co-primary endpoints were defined as follows:

- mean change in body weight over 12 weeks
- mean change in 5-IASS over 12 weeks.

With the fixed sample size of 158 patients per arm, study power was computed by means of simulations based on patients participating to previous company trials comparing anamorelin and placebo. Data from these trials were resampled in an unbalanced and in a balanced way with respect to 5-IASS at baseline (<= or >10), as those studies were not stratified and were unbalanced between treatment groups in terms of 5-IASS. To explore the power of the test procedure for the new endpoint, many scenarios to set assumptions for missing data were simulated, based on choices between different options for the following topics:

- The patient's baseline characteristics of the sample to be obtained (with BMI≤20, ACS-12≤37, 5-IASS≤17, fulfilling inclusion criteria 4 and 5, with/without missing data at baseline, with/without 5-IASS missing at week 3)
- The kind of imputation method adopted (fully MAR or MNAR+MAR based on predefined rules)

- The variables to be included as covariates in the imputations (from a large number to no covariates)
- The process for the MNAR+MAR imputation method: the different sets of subjects contributing to the imputations (all subjects with data vs. all complete subjects) and different sequential steps for applying MAR and MNAR
- The method of analysis (ANOVA with the 5-IASS stratum included in the ANOVA model, then including/excluding in the model the baseline covariate of the variable under analysis)

For each scenario the number of simulated studies ranged from 400 to 1000.

The simulations showed a power close to 100% to test an effect size in terms of mean change in body weight over 12 weeks approximately equal to 1.8 kg. The power to test an effect size in terms of mean change in 5-IASS over 12 weeks within the range of 1.2 - 1.4 was showed to range between 78% and 87%. This leads to a joint power for the two co-primary endpoints of at least 78%.

7.3. Statistical Testing

Business & Decision

Life Sciences

The primary and the secondary efficacy endpoints will be evaluated using a hierarchy for testing in order to control type I error rate. The order of testing will be as follows:

- The mean change in body weight over 12 weeks (H0w) and the mean change in 5-item Anorexia Symptom Subscale over 12 weeks (H0_A), assessed as coprimary endpoints; Definition and derivation of the co-primary efficacy endpoints is given in Section 10.1.1.
- The secondary efficacy endpoint related to the duration of treatment benefit over 12 weeks in body weight gain (≥ 0 kg) (H0_{d0W}).
- The secondary efficacy endpoint related to the duration of treatment benefit over 12 weeks in body weight gain (≥ 1.5 kg) (H0_{dtw}).
- The secondary efficacy endpoint related to the duration of treatment benefit over 12 weeks in 5-item Anorexia Symptom Subscale (≥0 points) (H0_{d0A}).
- The secondary efficacy endpoint related to the duration of treatment benefit over 12 weeks in 5-item Anorexia Symptom Subscale (≥ 3 points) (H0_{dtA}).
- The secondary efficacy endpoint related to the mean change in FAACT 12-item A/CS domain score from baseline over 12 weeks (H0_{mF}).
- The secondary efficacy endpoint related to the mean change in FACIT-F $(H0_{mFF})$ from baseline over 12 weeks.
- The secondary efficacy endpoint related to the mean change in FAACT total score (H0_{mFt}) from baseline over 12 weeks.

Definition and derivation of the secondary efficacy endpoints is given in Section 10.2.1. Each of these tests will be done sequentially at the level of 0.05 bilateral. HELSINN

7.3.1. Testing the co-primary endpoints

To preserve the experimental Type I error rate (threshold of 0.05 two-sided), in order to declare the test component (anamorelin) superior to the placebo, both co-primary endpoints must be significant, meaning that both $H0_w$ and $H0_a$ must be rejected simultaneously.

- The null hypothesis for the first co-primary endpoint of mean change in body weight from baseline over 12 weeks (H_{0w}) and the corresponding alternative hypothesis (H_{1w}) are defined as:

 H_{0w} : $MW_a = MW_p$

Business & Decision

Life Sciences

H_{1w}: MW_a ≠ MW_p

Where MW_a is the mean change in body weight from baseline over 12 weeks for the anamorelin arm and MW_p is the mean change in body weight from baseline over 12 weeks for the placebo arm.

- The null hypothesis for the other co-primary endpoint of mean change from baseline over 12 weeks in patient 5-item Anorexia Symptom Subscale (H_{0A}) and the corresponding alternative (H_{1A}) are defined as:

 H_{0A} : $MA_a = MA_p$

 H_{1A} : $MA_a \neq MA_p$

Where MA_a is the mean change from baseline over 12 weeks in 5-item Anorexia Symptom Subscale for the anamorelin arm and MA_p is the mean change from baseline over 12 weeks in 5-item Anorexia Symptom Subscale for the placebo arm.

7.3.2. Testing the secondary endpoints

- The null hypothesis concerning the first secondary endpoint of duration of treatment benefit over 12 weeks in body weight (≥0 kg) ((H_{0d0w}) and the corresponding alternative hypothesis (H_{1d0w}) are defined as:

 H_{0d0w} : $D_0W_a = D_0W_p$

 H_{1d0w} : $D_0W_a \neq D_0W_p$

Where D_0W_a is the duration of treatment benefit over 12 weeks in body weight gain (≥ 0 kg) for the anamorelin arm and D_0W_p is the duration of treatment benefit over 12 weeks in body weight gain for the placebo arm.

 H_{0d0W} will be tested using a two-sided Type-I error threshold of 0.05 only if both H_{0w} and H_{0a} (i.e., the null hypothesis concerning the primary endpoints) are rejected.

 The null hypothesis concerning the secondary endpoint of duration of treatment benefit in body weight over 12 weeks (≥ 1.5 kg) (H_{0dtw}) and the corresponding alternative (H_{1dtw}) are defined as:

> H_{0dtW} : $D_tW_a = D_tW_p$ H_{1dtW} : $D_tW_a \neq D_tW_p$

20/66

Where D_tW_a is the duration of treatment benefit over 12 weeks in weight (≥ 1.5 kg) for the anamorelin arm and D_tW_p is the duration of treatment benefit over 12 weeks in weight for the placebo arm.

 H_{0dtW} will be tested using a Type-I error threshold of 0.05 two sided only if H_{0d0W} (i.e., the null hypothesis concerning the first secondary endpoint) is rejected; note the latter rejection requiring the rejection of if both H_{0w} and H_{0a} .

- The following hypothesis systems will then be tested based on the rules above described.

 H_{0d0A} : $D_0Aa = D_0A_p$ H_{1d0A} : $D_0A_a \neq D_0A_p$

Business & Decision

Life Sciences

Where D_0A_a is the duration of treatment benefit over 12 weeks in 5-item Anorexia Symptom Subscale (≥ 0 points) for the anamorelin arm and D_0A_p is the duration of benefit over 12 weeks in 5-item Anorexia Symptom Subscale for the placebo arm.

 H_{0dtA} : $D_tAa = D_tA_p$ H_{1dtA} : $D_tAa \neq D_tA_p$

Where D_tA_a is the duration of treatment benefit over 12 weeks in 5-item Anorexia Symptom Subscale (\geq 3 points) for the anamorelin arm and D_tA_p is the duration of benefit over 12 weeks in 5-item Anorexia Symptom Subscale for the placebo arm.

 $H_{0mf}: MF_a = MF_p$ $H_{1mf}: MF_a \neq MF_p$

Where MF_a is the mean change from baseline over 12 weeks in FAACT 12-item A/CS domain score in the anamorelin arm and MF_p is the mean change from baseline over 12 weeks in FAACT 12-item A/CS domain score in the placebo arm.

Similar hypothesis systems are set-up for FACIT-F (H_{0mFF}, H_{1mFF}) and FAACT total score (H_{0mFt}, H_{1mFt}).

8. GENERAL CONSIDERATION FOR STATISTICAL ANALYSIS

8.1. Descriptive Statistics

All analyses will be conducted using SAS version 9.4 or higher.

The following conventions will be used when presenting summary statistics:

- Continuous variables will be summarized using the following descriptive statistics: number of subjects (n), mean, standard deviation (SD) median, minimum (min), maximum (max), 25th percentile (lower quartile or Q1) and 75t^h percentile (upper quartile or Q3).
- Categorical and binary variables will be summarized by the number of subjects (n) and the percent of subjects in each category. For AE tables, the number of events (E) will also be presented. Percentages will be presented to 1 decimal place.
- The number of subjects or observations will be presented as an integer.
- Mean, lower quartile and upper quartile will be presented to 1 decimal place more than the raw value.
- Min, max and median will be presented to the same number of decimal places as the raw value.
- Standard deviation will be presented to 1 decimal place more than the mean value, up to a reasonable number of decimal places (i.e., rarely more than 3 decimal places unless the nature of the data suggests this).
- The denominator for percentage calculations will be the number of non-missing observations at that visit. Where this isn't appropriate, the number of subjects in the relevant analysis set will be used.

8.2. Addressing intercurrent events

8.2.1. Intercurrent event death

The data from the previous trials HT-ANAM-301 (4) and HT-ANAM-302 (5) suggest a positive effect of anamorelin on the weight and the 5-IASS. Death from underlying disease is rather inevitable in this target population and it is anticipated to not reflect a failure of study treatment. In accordance with the ICHE9 R1 guideline, the death is considered as an intercurrent event after which no value is measurable. In order to measure the treatment effect for these patients, the "while alive" strategy will be used. Therefore, for patients dying before the completion of the period, no imputation strategy will be adopted for outcomes after death and only values collected before death will be used for the evaluation of the endpoint.

8.2.2. Intercurrent event study drug discontinuation

The treatment policy strategy will apply to address study drug discontinuation.

Due to the nature of the patients' underlying disease, a non-ignorable amount of missing data is expected in this trial. Every effort has been made to collect data from the protocol-specified assessments; patients were asked to continue to participate in the study and complete planned visits up to the end of the study period (Week 24) even if they have permanently discontinued treatment with the IMP ("retrieved dropout" approach).

Reason for treatment discontinuation will be collected in the CRF and will be considered for use in investigating possible unexpected patterns of missing data. To minimize the risk of bias in the analysis, specific rules for single/multiple imputation will be adopted

8.3. Handling of missing data

Business & Decision

Life Sciences

8.3.1. Efficacy Missing Data

The preferred statistical approach to manage the missing values due to the intercurrent event was the Multiple Imputation (MI) using retrieve dropouts (e.g.: assessments in patients no more under randomized treatment). However, at the BDRM it was confirmed that only a small number of retrieved dropouts was available, making unfeasible the established approach. For this reason, a control-based MI approach will be adopted by considering a Missing Not at Random (MNAR) mechanism for missing data: imputation of values in the active arm will be done using the non-missing values from the control group. This approach does not assume benefits for anamorelin in case of intercurrent event and limits a post-discontinuation clinical effect to that of placebo.

Efficacy missing data will be imputed on the bases of rules described in Appendix 12.1.

For missing data the imputation of the values will be done at the level of the visit for the raw values (for instance weight).

Post-discontinuation missing date of visit X will be imputed by adding 3 weeks to the date of the previous available visit X-1. The date of visit X+1 will be imputed by adding 3 weeks to the date of Visit X imputed in the previous step and so on.

Imputed values will then be used to derive primary, secondary and exploratory endpoints according to rules reported in Section 10.1.1, 10.2.1 and 10.3.1.

Datasets including imputed values and resulting derived variables will be used for all efficacy endpoints (primary, secondary and exploratory).

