10.1.1. Primary efficacy endpoint derivation

The mean change effect for both co-primary endpoints will be computed as sum of the changes from baseline over 12 weeks by the time of the last assessment (either week 12 or before in case of death), and then divided by the number of assessments (observed or imputed) from baseline up to the time of the last assessment (either week 12 or before, in case of death).

For the derivation of the 5 item Anorexia Symptom Subscale FAACT A/CS domain at each visit see Section 4.3.1 and Appendix 12.3.

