10.1.2. Primary efficacy analyses

The primary efficacy analyses will be conducted on the ITT set. Statistical hypothesis H_{0w} and H_{0a} , as defined in Section 7.3, will be tested using an Analysis of Variance (ANOVA) model including treatment group and the three stratification factors at randomization as categorical covariates, at a Type-I error threshold of 0.05 two-sided.

As anticipated in the beginning of this Section 10, inferential analysis will be done after imputation of missing data. An established number (N=100) of imputations will be

performed and for each of the imputation the ANOVA model will estimate treatment effect and the related standard error. The pooling of the estimates will be computed using the Rubin rule (1). The pooled effect and the related p-value will be interpreted for the primary efficacy analyses. In addition, the 95% confidence interval of the pooled difference and the least squares (LS)-mean with the 95% confidence interval will be presented per treatment group.

More details for the multiple imputation process are described in Appendix 12.1.

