12.1.1.2. Imputation rules for Non-intermittent missing values (monotonic missingness)

Imputation rules for non-intermittent missing values are based on a main rule and some exceptions.

The rule and the exceptions will be applied separately for each efficacy parameter.

Main rule

All missing values will be imputed assuming MNAR, specifically by means of the control-based multiple imputation method.

Reason: Most of the patients are expected to have missing values from time of treatment stop. In addition, the patients under study are characterized by poor prognosis and the reasons for treatment discontinuation are expected to be more related to the background disease than to treatment failure. For this reason, it cannot be assumed that the values after the treatment discontinuation would follow the same trend as before discontinuation because the general conditions, with specific exceptions described below, after discontinuation get to worsen. The implementation of the control-based imputation is conservative because it assumes that the deterioration of the patient condition affects mainly the patients in the active treatment group.

Exceptions

- 1. Independent from reason for discontinuation of treatment, if:
 - at least two non-missing post-baseline assessments are available (first assessment = X_1 and last assessment = X_{last}) and,
 - X_{last} $X_1 \ge 0$ and $X_{\text{last}} \ge$ baseline,

then impute all the missing values with the MAR multiple imputation approach including randomised treatment as the covariate.

- 2. If reason for discontinuation of treatment = "Physician decision" or = "Withdrawal by subjects" and:
 - \circ at least two non-missing post-baseline assessments are available (first assessment = X1 and last assessment = X_{last}) and,
 - $\circ \quad X_{\text{last}} \text{ } X_1 \text{ < 0 and } X_{\text{last}} \text{ < baseline,}$

then impute all missing values to the worst value observed for the subject, considering only the on-treatment (post-baseline) timepoints.

Reasons:

Imputation for Exception 1

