This exception is applicable for any reason for discontinuation, when the trend reveals an improvement of the efficacy assessments over time, with the last post-baseline assessment (X_{last}) better than both the baseline and the first post-baseline assessment (X₁). Based on these conditions, it is assumed that the decision of stopping the treatment is not related to the treatment itself (since the efficacy parameter was improving over time). Due to the improvement over time, it can also be assumed that

the treatment effect would have been maintained as it was before interruption for the rest of the observation period. For this reason, the missing values after the treatment discontinuation will be imputed with the Missing at Random (MAR) multiple imputation approach including randomized treatment as the covariate. This approach might be slightly optimistic for values missing at visits far from the visit of the last assessment, however this will not impact the primary endpoint that is limited to week 12, considering that at least assessments at week 3 and at week 6 are requested by the rule.

Imputation for Exception 2

Business & Decision

Life Sciences

This exception is limited to the reasons of treatment discontinuation that are most likely related to lack of efficacy of the treatment; the criterion for considering the unknown values as related to lack of efficacy is the negative trend of the observed efficacy assessments over time, as documented by the last post-baseline assessment (X_{last}) worse than the baseline and the first post-baseline assessment (X_1). Based on these conditions, it is assumed that the decision of stopping the treatment can be related to the treatment itself (lack of efficacy). The missing values will be imputed with the worst value observed for the patient considering only the on-treatment (post-baseline) timepoints.

Final revision of the above rules was done at the BDRM and they have been confirmed.

The details of the process are showed in the following steps.

STEP 1: Single/Multiple imputations

- Impute all intermittent missing data
- Create 100 records for each value
- Application of the Main Rule:

Apply MNAR Control-Based imputation on all subjects (placebo and active treatment) with at least one missing assessment.

- MI on all non-intermittent missing

- only placebo patients contribute to the imputation.

Expectation after imputation: only 1 dataset including:

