- ANAM and placebo patients without missing data (all assessments observed)
- ANAM and placebo patients with at least 1 missing assessment imputed by the imputation process.

Note: it is theoretically possible that aberrant values are derived because of the imputation. Aberrant values are defined as follows:

- For each item of the questionnaires:
 - a) Imputed value < the lower limit (0)
 - b) Imputed value > the upper limit (4)
- \circ For the body weight:
 - a) Imputed value < the lower limit (30 Kg)
 - b) No upper limit for the Body Weight is fixed.

In the cases (a) the imputed value will be set equal to the lower value.

In the cases (b) the imputed value will be set equal to the upper value.

Unscheduled assessments of body weight and questionnaires are not considered for imputations. These values will be listed only (and have all ANL0XFLs set to blank).

 Application of Exception 1: Apply MAR (as correction to the previous control-based imputation on patients fulfilling Exception 1) *Note: Values to be imputed with MAR need first to be re-set at missing.* A flag before starting with the imputation process should identify the cases where the exception 1 should be applied. Imputed values after MAR imputation should be within the aberrant values described above for the MNAR imputation
 According to Exception 2: Impute worst value at subject level.

A flag before starting with the imputation process should identify the cases where the exception 2 should be applied. Worst value should be calculated before any imputation.

- The imputation process does not distinguish between missing due to treatment discontinuation and death. All imputed assessments after death must be set to missing.

No covariates, apart from treatment arm (as by variable or covariate, as relevant) and baseline value will be included in the MI models.

For each variable, 100 imputed values will replace each missing value.

The following variables will be separately imputed according to the above mentioned single or multiple imputation methods:

- Weight
- 5-IASS
- 4-item Anorexia Concerns Subscale (4-IACS)
- 12-item A/CS domain

Business & Decision

Life Sciences

- FAACT total score
- FACT-G total score
- FAACT TOI
- Functional Assessment of Chronic Illness Therapy-Fatigue (FACIT-F)
- FACIT-F TOI score

The PGIS and the PGIC endpoints and the hunger assessment will not be imputed.

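### SAP 8.3.1 describes the primary imputation as placebo-limited after discontinuation, but Exception 1, part of the same imputation, assumes that the effect is maintained

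*SAP*

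**What the plan says.** SAP 8.3.1 explains that the blinded review found too few retrieved dropouts, so a control-based method replaced the preferred one. It then states the property claimed for that method: "This approach does not assume benefits for anamorelin in case of intercurrent event and limits a post-discontinuation clinical effect to that of placebo". It refers to Appendix 12.1 for the rules. So does the primary analysis in 10.1.2: "More details for the multiple imputation process are described in Appendix 12.1".

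For monotone missing values, Appendix 12.1.1.2 has a control-based main rule and two exceptions. Exception 1 applies whatever the reason for stopping treatment. It needs at least two post-baseline values, the last of them no lower than the first and no lower than baseline; "then impute all the missing values with the MAR multiple imputation approach including randomised treatment as the covariate". The ground given is that "the treatment effect would have been maintained as it was before interruption for the rest of the observation period". Step 1 places it after the main rule: "Apply MAR (as correction to the previous control-based imputation on patients fulfilling Exception 1".

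The appendix concedes slight optimism at visits far from the last observed one, but says "this will not impact the primary endpoint that is limited to week 12". The reason it offers is the minimum of observed data that Exception 1 demands: "considering that at least assessments at week 3 and at week 6 are requested by the rule". SAP 10.1.1 defines that endpoint as the changes from baseline summed, "then divided by the number of assessments (observed or imputed) from baseline up to the time of the last assessment". SAP 10.1.3.1 plans a sensitivity analysis that drops the exceptions.

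**The concern.** 8.3.1 is where the SAP explains and characterises its primary missing-data method; Section 13, which lists changes from the protocol, does not cover it. A reader will take from 8.3.1 that nobody in the anamorelin arm is credited with an anamorelin effect after stopping. For Exception 1 patients the opposite is assumed, and they are selected by their own observed improvement. Protocol 2.1.1 says the imputation is to reflect that patients have stopped treatment, so a maintained-effect assumption should be visible wherever the primary estimate is described.

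The assurance about Week 12 adds to this, because it tells the reader that the optimism need not be considered for the primary endpoint. At stake is how the primary estimate is described and interpreted, not whether the analysis can be carried out.

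**Working it through.** **1. Which rules feed the primary analysis.** 10.1.2 sends the primary analysis to Appendix 12.1, where the main rule and both exceptions sit in Step 1. Set against the 8.3.1 sentence:

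| Rule in 12.1.1.2 | Source of imputed values | Fits 8.3.1? |
|---|---|---|
| Main rule | Placebo patients only | Taken as yes |
| Exception 1 | MAR, randomised arm as covariate | No: effect assumed to persist |
| Exception 2 (physician decision or patient withdrawal, last value below baseline and below the first post-baseline value) | Patient's own worst on-treatment value | No benefit assumed, but not placebo-based |

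**2. Does Exception 1 reach the 12-week endpoint?** The post-baseline visits are Weeks 3, 6, 9 and 12. A patient last seen at Week 6 has two of the four changes imputed; one last seen at Week 9 has one. If MAR and control-based values differ by d per imputed visit, the patient's mean change moves by 2d/4 = d/2 or by d/4. It is unaffected only if d = 0.

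**3. How large?** The plan gives no figure for this. The sample-size figure with full inputs (CCR 7.5% against 20%, 158 per arm) reproduces at 90.1% power but has no bearing here. The co-primary power came from resampling with no SD stated. Pairing 1.2 points with 78% and 1.4 with 87% (my assumption), it implies a standard error for the 5-IASS difference of 1.2/(1.960 + 0.772) = 0.44 to 1.4/(1.960 + 1.126) = 0.45.

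I simulated the imputation with and without Exception 1.
- From the SAP: 158 per arm; effects averaging 1.3 points (middle of 1.2 to 1.4) and 1.8 kg.
- Assumed: SD per visit 4.6 points and 3.0 kg; correlation between visits 0.5 or 0.7; dropout of 8, 15 or 25% after each of Weeks 3, 6 and 9, unrelated to outcome; no deaths; Exception 2 left out; MAR step run on the control-based output with Exception 1 values reset.
- Missing at Week 12: 1 − 0.92³ = 22%, 1 − 0.85³ = 39%, 1 − 0.75³ = 58%.

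Estimated difference without → with Exception 1 (shift):

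| Correlation | Dropout | 5-IASS, points | Weight, kg |
|---|---|---|---|
| 0.5 | 8% | 1.236 → 1.250 (0.014) | 1.667 → 1.690 (0.023) |
| 0.5 | 15% | 1.131 → 1.152 (0.021) | 1.537 → 1.572 (0.035) |
| 0.5 | 25% | 1.019 → 1.042 (0.023) | 1.391 → 1.425 (0.034) |
| 0.7 | 8% | 1.228 → 1.237 (0.009) | 1.698 → 1.716 (0.018) |
| 0.7 | 15% | 1.166 → 1.180 (0.014) | 1.637 → 1.661 (0.024) |
| 0.7 | 25% | 1.096 → 1.109 (0.013) | 1.476 → 1.501 (0.025) |

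Hand check of the second row, 5-IASS: 9.6% of anamorelin patients met Exception 1 and d averaged 0.64 points. With constant dropout about 1/(1 + 0.85) = 54% of them were last seen at Week 6, giving 1.54 imputed visits each. The anamorelin mean moves by about 0.096 × 1.54/4 × 0.64 = 0.024. The placebo arm moves a little too, leaving the simulated 0.021.

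In relative terms the shift runs from 0.009/1.228 = 0.7% to 0.023/1.019 = 2.3% (5-IASS), and from 0.018/1.698 = 1.1% to 0.034/1.391 = 2.4% (weight). The largest 5-IASS shift is 0.023/0.44 = 0.05 standard errors.

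**4. Other assumptions.** A wider grid added deaths, outcome-related dropout, other correlations and larger effects. Exception 1 alone then shifted the difference by 0.001 to 0.024 points and 0.001 to 0.037 kg. If the MAR step instead reads the dataset named in the example code, the upper ends are 0.041 points and 0.062 kg. With no true effect the shift stayed within 0.003 points or kg. Type I error was 1.6 to 2.8% without the exceptions and 1.7 to 2.8% with both.

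**The case against.** The best defence is disclosure. The 8.3.1 sentence follows directly on the control-based method and is followed by a pointer to Appendix 12.1, which announces exceptions, states what Exception 1 assumes and admits some optimism. The rules were confirmed at the blinded review, and 10.1.3.1 removes the exceptions for both co-primaries. An analyst would program the right method, and the effect of the exceptions will be seen. All of this stands. It confines the point to how the primary estimate is described.

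The Week 12 assurance can also be read narrowly. Its subject is optimism at distant visits, and Weeks 9 and 12 lie at most six weeks after a last value at Week 6. That supports expecting little effect; it does not support none.

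A reader might go further and infer that the 8.3.1 sentence fails even under the main rule, because imputation conditions on the patient's own earlier visits. The control-based code is incomplete in the available text, so I do not rely on this. Nor does the mismatch in 12.2.1.2 between the dataset named in the example call and the one named in its note leave the method open. Section 12.2 calls the code only an example, and Step 1 and the note both have the MAR step correct the control-based output.

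**Conclusion.** The point holds as a fault of description. The primary analysis as specified does not have the property that 8.3.1 claims, and the assurance in 12.1.1.2 is stronger than the endpoint definition allows.

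The numerical effect is small, and towards anamorelin when a benefit exists. Only direction and rough size should be relied on. The share of missing anamorelin values falling under Exception 1 was 16 to 24% in the tabulated runs but 5 to 16% in the wider grid, because dropout, SD and correlation are all assumed.

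Two stronger conclusions are not supported. One is that the exceptions inflate type I error: the no-effect runs showed nothing of the kind, and Exception 1 applies in both arms. The other is that the analysis without exceptions must become primary. Protocol 9.4.5.2.1 assigns control-based imputation to sensitivity analysis, and Protocol 9.4.1 foresaw special imputation rules.

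**What to change.** 1. In SAP 8.3.1, limit the no-benefit sentence to the main rule. State that Exception 1 patients are imputed under MAR by randomised arm with the effect assumed maintained, and that Exception 2 patients receive their worst observed on-treatment value. Do not call the primary estimate placebo-limited.
2. In 12.1.1.2, replace the assurance about the primary endpoint with a statement that the effect is expected to be small and is assessed by the 10.1.3.1 analysis.
3. Report the 10.1.3.1 result beside the primary result for each co-primary, with the number of patients per arm imputed under each rule. The rules apply separately to weight and 5-IASS, so the counts should too.

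Extending 10.1.3.1 to the secondary endpoints, which share this imputation, is optional; neither document requires it. Aligning the example dataset name in 12.2.1.2 with its note is a footnote. If the data are already unblinded, the same clarifications belong in the study report.

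The cost is two text edits and one extra table, with a slightly less favourable description of the primary estimate. The primary analysis itself does not change.
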